4.8 Randomisation and allocation

Eligible participants, who have signed the informed consent form, will be randomised to one of the two study groups in a 1:1 allocation ratio. A randomisation application hosted by CHaRT will be used for this purpose. This is available 24 hours a day by means of a web-based randomisation application. Random allocation will use a stratification algorithm based on:

- collaborating centre
- type of urinary incontinence (pure Stress Urinary Incontinence or stress-predominant mixed urinary incontinence)

The type of urinary incontinence will be as per the HCP assessment at the time of review at the clinic.

Consenting patients will be randomised to VCDs plus PFMT or to PFMT-only as close as possible to receiving the interventions. Participants in the VCD plus PFMT arm will be prescribed and/or start using their VCDs at the time (or as close as practically possible) to their first physiotherapy appointment.

A person with delegated authority will access the web-based system. The trial is not blinded - at randomisation, an email will be sent to the collaborating site research team, including the PI, and the trial office, informing them of the allocation.

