7.2 Trial specific considerations

Planned hospital visits for conditions other than those associated with urinary incontinence and/ or its treatment will not be collected or reported. Further UI treatment will be recorded as a secondary outcome measure, but will not be reported as serious adverse events.

In this trial, AEs that are potentially related to the trial procedures and interventions (VCDs, PFMT) will be recorded (see definition of “related” in section 7.5 below). **All serious related AEs will be recorded as SAEs.** Any deaths (any cause) will also be recorded as SAEs. We will not capture unrelated SAEs.

Due to the reporting and collection of these events as primary and secondary outcome measures, the following do not need to be reported as AEs or SAEs:

- Urinary symptoms
- Sexual dysfunction

Furthermore, pre-existing conditions and any pre-planned hospitalisations (e.g. elective surgery) not associated with clinical deterioration will not be classed as Serious Adverse Events.

Trial specific expected adverse events

The FEEL-GOOD trial involves interventions to treat stress urinary incontinence which are well established in clinical practice. Expected adverse events arising from PFMT and VCD usage are:

- pelvic or abdominal pain/ discomfort,

- low back pain
- vaginal pain/ discomfort/ irritation
- vaginal discharge/ ulceration or Smell,
- abnormal vaginal bleeding,
- bleeding during removal of the device
- urinary or vaginal infections,
- urinary retention requiring a catheter in the bladder
- VCD falling out
- VCD entrapment in the vagina requiring removal in theatre

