7.5 Evaluating AEs and SAEs

All adverse events will be assessed in respect of seriousness, relationship to study intervention, whether expected or unexpected, and therefore, whether constituting a Serious Adverse Event (SAE) by the local PI, CI or their deputies.

Assessment of Seriousness

The Investigator should make an assessment of seriousness as defined in Section 7.1.

Assessment of Causality

The Investigator must make an assessment of whether the SAE is likely to be related to any of the research procedures according to the following definitions:

- Related: resulted from any of the procedures required by the protocol, whether or not this procedure is the specific intervention under investigation and whether or not it would have been administered outside the study as normal care.
- Unrelated: where an event is not considered to be related to any of the research procedures.

Assessment of Expectedness

Expectedness will be assessed for events using the list of expected events listed in Section 7.2.

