9.2 Gantt chart

10. STATISTICAL ANALYSIS

The statistical analysis is outlined fully in a separate statistical analysis plan. All main analyses will be based on the Intention-to-Treat (ITT) principle. Analysis will take place after full recruitment and follow-up is complete. The focus will be on tabulated and associated graphical summaries of the key indicators of success of the pilot.

We will report data in line with the Consolidated Standards of Reporting Trials (CONSORT) 2010 extension statement for Pilot and Feasibility trials showing attrition rates and loss to follow-up.

As the primary outcome is the feasibility of achieving 80% of the target within 6 months it is a simple summary of the number of participants recruited and there is no uncertainty on this count. The number identified as eligible is also an exact number as are the numbers who drop out from receiving the intervention, withdraw consent and fail to provide follow-up data. These numbers can be used to calculate the percentage of eligible participants who enter the trial, adhere to their allocated intervention and also estimate the loss to follow-up percentage. Confidence intervals will be obtained for these percentages too.

The success rate from the PGI-I, adverse events will be summarised with count and percentage while the specific UI outcomes and waiting time for physiotherapy will be summarised with mean and standard deviation. The UI outcomes and PGI-I success rate will be compared using the appropriate linear regression model with adjustment for the baseline outcome where possible to obtain a treatment effect and 95% confidence interval. Adverse event rates will be compared between the groups using the appropriate linear model to obtain a relative risk.

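### Adverse events are recorded only if judged potentially related, with allocation known, and are then compared between arms by relative risk, so unequal attribution can move that ratio away from 1

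*Protocol*

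**What the plan says.** **Recording.** Protocol section 7.2 states that "AEs that are potentially related to the trial procedures and interventions (VCDs, PFMT) will be recorded". Of serious events it adds: "We will not capture unrelated SAEs"; deaths from any cause are the exception. Section 7.3 limits the duty to document to events that meet the section 7.2 criteria, and section 7.4 speaks of recording relevant events.

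**Who judges, and with what knowledge.** Section 4.8 says: "The trial is not blinded - at randomisation, an email will be sent to the collaborating site research team, including the PI, and the trial office". Section 7.5 has adverse events assessed for seriousness, relationship and expectedness, and so "whether constituting a Serious Adverse Event (SAE) by the local PI, CI or their deputies". No blinded assessor is named. The definition is wide: "Related: resulted from any of the procedures required by the protocol, whether or not this procedure is the specific intervention under investigation".

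**Expected events.** Section 7.2 gives one list of ten entries for PFMT and VCD use together. Three need a device: "bleeding during removal of the device", the VCD falling out, and "VCD entrapment in the vagina requiring removal in theatre".

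**Analysis.** Section 10 summarises adverse events by count and percentage and then adds: "Adverse event rates will be compared between the groups using the appropriate linear model to obtain a relative risk". It does not say whether the events compared are those reported by participants or those left after the relatedness judgement, and it does not separate the device-specific events.

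**The concern.** A between-arm relative risk is interpretable when events are ascertained in the same way in both arms. Here an event enters the record only after someone who may know the allocation has judged it potentially related. Vaginal infection, discharge, irritation or pelvic pain can plausibly be put down to a device sitting in the vagina more readily than to an exercise programme. If that happens, the same event counts in one arm and goes unrecorded in the other, and the ratio moves without any difference in what the women experienced.

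This is a rule about data capture. The separate statistical analysis plan can choose which recorded events to analyse, but it cannot recover events that section 7.2 left unrecorded.

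At stake is the pilot's comparative safety estimate. Section 5.2 lists adverse events of VCDs among the secondary outcomes.

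**Working it through.** **Inputs from the protocol.** 74 women, 37 per arm (section 4.1); 20% attrition (section 9.1), so 74 × 0.8 = 59.2, or about 30 per arm followed up. The protocol states no adverse event rate, attribution rate or adverse event relative risk, so there is no figure of its own to reproduce.

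**Assumed inputs, for illustration only.**
- p: risk of an event possible in either arm, equal in both arms (no true difference); 0.30 where a value is needed.
- a: share of such events recorded in the PFMT-only arm, 1.0 down to 0.5; the share in the VCD arm is set at 1.
- d: risk of a device-specific event in the VCD arm, 0 to 0.20.

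**Step 1, attribution alone.** Recorded RR = (p × 1)/(p × a) = 1/a. The background risk p cancels.
- a = 1.0: RR 1.00
- a = 0.9: 1/0.9 = 1.11
- a = 0.75: 1/0.75 = 1.33
- a = 0.5: 1/0.5 = 2.00

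**Step 2, pooling device-specific events, with equal attribution (a = 1).** RR = [1 − (1 − p)(1 − d)]/p, with p = 0.30.
- d = 0.05: 0.335/0.300 = 1.12
- d = 0.10: 0.370/0.300 = 1.23
- d = 0.20: 0.440/0.300 = 1.47

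This excess is real. It reflects harms of adding a device, but it is mixed with events that can occur in both arms.

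**Step 3, both together.** With p = 0.30, a = 0.75 and d = 0.10: 0.370/(0.30 × 0.75) = 0.370/0.225 = 1.64. A reader of the pooled ratio could not tell which part is device harm and which part is attribution.

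**Step 4, precision.** SE of log RR = √[(1 − p1)/(n p1) + (1 − p0)/(n p0)], where p1 and p0 are the recorded risks in the VCD and PFMT-only arms, with n = 30 per arm.
- p1 = p0 = 0.30: SE = √(2 × 0.7/9) = 0.394. The 95% interval runs a factor of exp(1.96 × 0.394) = 2.17 either side of 1.
- p1 = 0.30, p0 = 0.15 (a = 0.5): SE = √(0.7/9 + 0.85/4.5) = 0.516, a factor of 2.75. The interval around 2.00 is 2.00/2.75 = 0.73 to 2.00 × 2.75 = 5.50.

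A bias of this size would usually lie inside the interval. It would still shift the point estimate.

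**The case against.** The strongest reply is that both arms already receive the same enquiry. Section 4.9 sends the questionnaires to all randomised women whatever their compliance and asks for side effects. Table 2 collects adverse events at 3 and 6 months, and section 7.3 says the questionnaires ask about any event, hospital admission or healthcare contact. This stands as a partial safeguard. It removes the problem only if those reports enter the comparison before the relatedness judgement. Section 7.3 points the other way by tying documentation to section 7.2, and section 10 is silent.

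Second, the filter is wide. The threshold is potential relatedness, PFMT counts as well as the VCD, and the expected events are listed for both interventions jointly. The detailed causality rule in section 7.5 is also written for serious events. All of this is true, and it makes a large imbalance less likely. A definition that is the same for both arms does not guarantee equal application by assessors who know the arm.

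Third, the choice of event types for the ratio is ordinary analysis-plan content, and that plan is not shown. This holds for separating the device-specific events. It does not hold for events never recorded.

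A reader might go further and infer that the plan is bound to produce a VCD excess, or that a ratio including device-specific events is infinite or meaningless. The documents support neither. Unequal attribution is plausible but not shown. Device-specific events are genuine harms, and a pooled ratio is finite once the PFMT-only arm has any event. Only an event-specific ratio with no events in that arm cannot be estimated. Even that zero is not certain, because section 4.10 allows for women receiving the non-allocated intervention and section 4.11 notes that devices can be bought without prescription.

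**Conclusion.** The point holds as a risk that the protocol leaves open. A relatedness filter applied with allocation known stands ahead of a between-arm relative risk, and the text does not say that the common questionnaire reports bypass it. With no true difference, attribution alone would give a relative risk of 1.11 to 2.00 if 90% to 50% of PFMT-only events are recorded against all VCD-arm events, and 1.00 if attribution is equal. These are ratios of assumed shares, not predictions.

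The consequence is limited. Adverse events are a secondary outcome and do not appear in the progression criteria of Table 1, so the feasibility conclusion is unaffected. Nor do the documents say that this ratio will be carried into the patient information for a later trial, so that inference should not be drawn. The amendment is still worth making, because it takes an allocation-aware judgement out of a between-arm comparison at small cost.

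**What to change.** Amend sections 7.2, 7.3 and 10 together:

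- Record the seven expected event types possible in both arms from the same 3- and 6-month questionnaire items in both arms, regardless of attribution. They are pelvic or abdominal pain; low back pain; vaginal pain or irritation; vaginal discharge, ulceration or smell; abnormal vaginal bleeding; urinary or vaginal infection; and urinary retention needing a catheter.
- Base the between-arm relative risk on these events, taken before any relatedness judgement.
- Report the three device-specific events (bleeding on removal, VCD falling out, VCD entrapment) separately, as count and percentage among VCD users and as genuine device harms, outside the relative risk.
- Keep the relatedness judgement for serious adverse event reporting.

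The cost is a change of wording and, if the questionnaires do not already list these events, a few tick-box items. The questionnaires already go to both arms, so no new contact is needed. The downside is that more non-serious events are recorded and have to be entered and tabulated.

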10.1 Integration of data

The findings from Stage 1 qualitative study will be used to generate an initial set of deductive codes (grounded in the Theoretical Framework of Acceptability) and inductive codes relating to recruitment, randomisation and study outcomes to inform the design of Stage 2 Pilot RCT. Deductive content coding and inductive generation of new sub-codes will then form the first stage of analysis of the Stage 2 data. This will then be followed by matrix driven coding to complete the integrated analysis of Stage 1 and Stage 2 data. NIVIVO will be used to support rigour.

11. ORGANISATION: TRIAL MANAGEMENT AND OVERSIGHT ARRANGEMENTS

11.1 Trial office in Aberdeen

The Trial Office is in the Centre for Healthcare Randomised Trials (CHaRT) based within the Health Services Research Unit, University of Aberdeen and provides day to day support for the clinical centres. The Trial Manager in CHaRT and the NRS Fellow (MD) will take responsibility for the daily transaction of study activities. The data co-ordinator will provide clerical support to the trial, including organising all aspects of the postal questionnaires (tracking, mailing, and entering returned data using the trial web data entry portal). The CHaRT Quality Assurance Manager will supervise that CHaRT's standard operating procedures for trials are being followed, including adherence of the appropriate principles of GCP.

At the centres, the recruitment coordinators/ research nurses will be responsible for all local processes involved in identifying, consenting, and randomising the participants, along with facilitating the delivery of the intervention.

The FEEL-GOOD Study Office Team will meet regularly during the course of the study to ensure streamlined running and trouble-shooting.

11.2 Local organisation in sites

The local PI and research nurse in each site are responsible for all aspects of local organisation including identifying, consenting, and randomising participants as well as completing and maintaining appropriate documentation and notifying any challenges or unexpected changes during the trial. They will be responsible for ensuring that study data is collected for baseline assessments, gathering and recording participant study data on study specific Case Report Forms and will log all the details onto the remote web-based data capture system as soon as practical after completion. The local PI will return all study documents to the study office in Aberdeen when requested

Appropriate members of the local team are knowledgeable about the Protocol and will have appropriate Good Clinical Practice (GCP) training if applicable. Those members of the local team who are carrying out their routine activity as part of the study (for example physiotherapists involved in delivering PFMT) are not required to have GCP training. They can be added to the delegation log if they wish to be included. The local team is also responsible for notifying SAEs to the Trial Office (see section 7).

11.3 Project Management Group (PMG)

The trial will be supervised by the FEEL-GOOD Project management Group (PMG). This consists of the grant holders and representatives from the Trial Office. The PMG will meet/teleconference every 3 months on average. In addition, the PMG will also meet at the annual Trial Steering Committee meeting.

11.4 Trial Steering Committee (TSC)

A Trial Steering Committee (TSC), with independent members, oversees the conduct and progress of the trial. The TSC Charter documents the terms of reference of the TSC, the template for reporting and the names and contact details of members of the TSC. This Charter is filed in the Trial Master File (TMF).

11.5 Patient and Public Involvement (PPI)

We undertook an extended PPI focus group session, at the conception of the proposal and integrated their valuable suggestions. We worked closely with Women's Voices (RCOG) and Bladder Health-UK in the co-development of this proposal. They will form a patient advisor group (PAG) to drive our PPI partnership and play an active role in the design, recruitment, delivery, analysis and dissemination of the study. Both our PPI partners have patient representatives from diverse

backgrounds including age, ethnicity and socio-economic status. The PAG will ensure the research is centred on the needs of the women with UI through co-designing the patient interview questions and the HCP focus group questions. The PAG will also identify and support two members of the PAG to act as peer advocates. Our PPI will be part of the Project Management Group. All PPI will receive any training they need and will be reimbursed in line with NIHR guidance and the RCOG PPI tariff.

With the PPI members we will develop a public dissemination strategy that use a range of methods and formats including newsletters, podcasts, infographics, etc. The patient community will be informed by study newsletter and infographics, and the broader public via our PPI partner organisations' channels of communication e.g. social media, and advocacy events.

12. RESEARCH GOVERNANCE, DATA PROTECTION AND SPONSORSHIP

12.1 Research Governance

CHaRT is a fully registered Clinical Trials Unit with specific expertise in running multicentre RCTs. The study will be run under the auspices of CHaRT based at the Aberdeen Centre for Evaluation, University of Aberdeen. This supports compliance with Research Governance and the principles of GCP, and provides centralised trial administration, database support and statistical analyses.

The PMG will ensure via TSC that adequate systems are in place for monitoring the quality of the trial and that reports are prepared to a level suitable to the risk assessment of the trial.

12.2 Data protection

Data collected during the research will be kept strictly confidential and accessed only by trial team members. Data may be looked at by individuals from the Sponsor organisation or NHS sites where it is relevant to the participant taking part in this trial.

The trial staff involved with this project will comply with the requirements of the UK Data Protection Laws. The HRA recommended wording to fulfil transparency requirements under the GDPR for health and care research has been included in the PIL.

The CI and trial staff based in Scotland will also adhere to the current version of the NHS Scotland Code of Practice on Protecting Patient Confidentiality. Access to collated participant data will be restricted to the CI and appropriate trial staff.

Computers used to collate the data will have limited access measures via usernames and passwords.

Remote access to the network will be subject to robust authentication, and VPN (Virtual Private Network) connections to the network are only permitted for authorised users, ensuring that use is authenticated, and data is encrypted during transit across the network. No personal data will be downloaded or stored on local hard drives. All data input/access will be via the VPN and/or secure website.

Published results will not contain any personal data that could allow identification of individual participants.

The CHaRT senior IT development manager (in collaboration with the CI) manages access rights to the data set. Participants are allocated an individual trial number which is used to identify questionnaires and case report forms.

We anticipate that anonymised trial data may be shared with other researchers to enable international prospective meta-analyses. Consent will be sought for this.

12.3 Sponsorship

The University of Aberdeen is the sponsor for the trial.

13. ETHICS AND REGULATORY APPROVALS

Research Ethics Committee and appropriate NHS R&D approvals will be obtained prior to the commencement of recruitment. The trial will be conducted according to the principles of Good Clinical Practice provided by Research Governance Guidelines and any appropriate NHS R&D approvals will be obtained. The End of Trial declaration, and a final report are submitted to the Sponsor and the REC within the timelines defined in the regulations.

13.1 Protocol compliance and amendment

The Investigators will conduct the trial in compliance with the Protocol given favourable opinion by the NHS Research Ethics Committee. Any amendment to the Protocol or other approved documents will be reviewed by Sponsor (and funder where appropriate) before application to REC and R&D unless in the case of urgent safety measures when the Sponsor is notified as soon as possible. Sponsor will advise if an amendment is substantial / non-substantial and which review bodies need to receive it. Any deviations from the Protocol will be fully documented.

14. MONITORING AND AUDIT

The trial is monitored to ensure that it is being conducted as per protocol, adhering to Research Governance, the principles of GCP, and all other appropriate regulations. The approach to, and extent of, monitoring is specified in the trial monitoring plan and is appropriate to the risk assessment of the trial. Investigators and their host institutions are required to permit trial related monitoring and audits to take place by the Sponsor and/ or regulatory representatives, providing direct access to source data and documents as requested.

14.1 Risk assessment

An independent risk assessment has been carried out by the sponsor.

15. FINANCE AND INSURANCE

The trial is funded by a grant awarded by the Chief Scientific Office (CSO). The necessary clinical trials insurance is provided by the University of Aberdeen.

16. END OF TRIAL

The end of follow-up for each participant is defined as the final data capture on that individual. The end of the trial is defined as the end of funding.

The end of the trial will be reported to the Sponsor and REC within 90 days, or 15 days if the trial is terminated prematurely. If terminated prematurely, the Investigators will inform participants and ensure that the appropriate follow up is arranged for all involved, if appropriate.

A summary report of the trial will be provided to the Sponsor and REC within one year of the end of the trial. An end of trial report should also be issued to the funders at the end of funding.

